28.0 Process to Document Consent in Writing

As stated previously, all participants will provide written informed consent to partake in the study.

Handling of Study Documents. Study source documents, including but not limited to signed informed consent forms, completed eligibility checklists, and participant questionnaires, will be scanned and stored digitally as certified copies on a secure drive only available for access to trained study staff working with the documents. The drive will be only accessible with proper invitation to the drive by the Principal Investigator through their Partners account, which will require personal username and password information to access. Trained study staff will follow specific standard operating procedures for handling source documents and certifying each copy appropriately. The procedures are as follows. After source documentation is filled out by the participant, study staff will collect the original source document. The study staff member scanning documents will be kept as consistent as possible throughout the duration of the study to ensure uniformity among source documentation handling. Location, time, and date of the scanning of the document will be recorded at the time of scanning. Study staff will fill out the Source Documentation Certified Copy Cover Sheet (Appendix 30.22) and include this as the first page of the electronic version of the source document. After the source document is scanned and the corresponding electronic document is confirmed to be legible, all facing the correct direction, and together as a single document, it will be collected and destroyed immediately. Study staff will destroy the original copy of the source document by following MGH procedures of destroying documents with Personal Health Information (PHI). Electronic versions of source documents will allow study staff to access these documents regardless of where the original copy is stored, which may be inconvenient, increase study staff burden, and study cost if storage of documents is far from the location where research activities will be conducted or required to be placed in long term storage. This process has been developed streamlined, and successfully implemented in DF/HCC Protocol #17-201. If a patient is consented electronically, the completed version of their digital consent form will be saved as the completed, original source document and no certified copy cover sheet will be used.

30.1 Clinician Approach Email

Clinician Opt-out Email Template

Symptom-Targeted Randomized Intervention for Distress and Adherence
PI: [name].

Dear [Dr./NP/PA PROVIDER NAME],

I am a research coordinator working with [name] on a symptom-targeted randomized study for symptom management, distress, and adherence among breast cancer survivors on adjuvant endocrine therapy.

Your patient(s) may be eligible for the study:

Name	MRN	DOB

I would like to approach her regarding the study. Please let me know at your earliest convenience if I should refrain from approaching this patient for any reason. If I do not hear from you, I will follow-up to request permission.

Study participation does not preclude you and the rest of the patient's care team from medically treating the patient's symptoms per your clinical judgment.

Please feel free to let me know if you have any questions or concerns. Additionally, I have included a brief attachment with more study information.

Thank you,

(name of study staff)

Symptom-Targeted Randomized Intervention for Distress and Adherence among Breast Cancer Survivors on Adjuvant Endocrine Therapy (STRIDE):

A pilot feasibility trial
K07 Funded by the National Cancer Institute
PI: [name].

Study Rationale

- This study aims to enhance adherence, improve symptom management, and reduce distress among early-stage breast cancer survivors taking adjuvant endocrine therapy (AET)
- AET improves clinical outcomes for hormone-sensitive breast cancer, yet adherence among survivors is poor
- Barriers to adherence are well-established and modifiable; including concerns about adverse side effects, low appraisal of recurrence risk and need for therapy, and high distress (anxiety or depressive symptoms)
- Surprisingly, few interventions have been tested to promote adherence to AET, and none have addressed these modifiable factors
- Based on a qualitative study with breast cancer survivors, experts in hormonal symptoms, breast oncology clinicians, and behavioral psychologists, we developed a patient-centered, evidence-based intervention to improve symptom management, mitigate distress, and enhance AET adherence

Study Specifics

- This is a pilot randomized controlled trial in which patients will be randomized to receive either the STRIDE intervention or usual care
- The intervention consists of 6, one-hour sessions delivered over videoconferencing with a psychologist, psychology trainee/fellow, or social worker and two check-in phone calls (15-30 minutes)
- Patients in the control group will receive care as usual
- All patients will be asked to store their AET in study-provided, electronic pill bottles to monitor adherence and complete assessments at baseline, 12 weeks, and 24 weeks after enrollment

What Is Needed from You as the Clinician?

- Approve or deny study staff request to approach potentially eligible participants
- Refer patients you think may be eligible and a good fit for the study
- Provide care as usual

Patient Inclusion and Exclusion Criteria

- Female, age 21 or older, ability to read and respond in English
- Lives within the state of Massachusetts
- Diagnosis of early-stage (stage 0-IIIb), hormone-receptor positive breast cancer
- Completed any primary treatment
- Eastern Cooperative Oncology Group (ECOG) performance status ≤ 2
- Within 1 week to 36 months of initiating AET and is currently taking AET
 - If took a recent break, has taken AET within the past two weeks
- May not be on another clinical trial requiring medication monitoring
- May not have psychiatric or cognitive impairment
- Is not currently undergoing active primary treatment for other cancer (i.e. advanced stage cancer)

Study Contact Information:

- Please send potentially eligible patients to the study coordinators, [name] ([contact]) or [name] ([contact]), or to the study PI, [name], at [contact]

0.3 Study Screening Script

Hi, my name is [study staff] and I am a research assistant in the Cancer Center at MGH. I work on a study you might be interested in. Your oncologist said it would be alright if we speak with you about this study. This study offers a program for women who are taking a hormonal therapy and consists of 6 weekly, small-group, virtual visits with a cancer center clinician to address any concerns or challenges you may be experiencing while taking this medication. These visits would take place over a secure videoconferencing software with up to 2 other breast cancer survivors who are also taking hormonal therapy. Does this sound like something you might be interested in?

Each question is scored on a scale of 0-10. The first question is, on a scale of 0 being not bothered at all to ten being extremely bothered, how bothered are you by side effects from your hormonal therapy?

My next question is, on a scale of 0 being not upset at all to ten being extremely upset, how upset are you by having to take hormonal therapy?

My last question is, on a scale of 0 being not difficult at all to 10 being extremely difficult, how difficult is it for you to take your hormonal therapy medication every day?

IF A SCORE OF 4 OR ABOVE ON ONE OR MORE: Thank you for going through those questions with me. It sounds like you would be a good fit for this study. The next step is to go through the consent form, which I can send you over email. What is the best email address to send it to?

IF A SCORE OF 3 OR LESS ON ALL THREE: Thank you for going through those questions with me. It sounds like you are doing well with taking the hormonal therapy medication right now and you screen out for the study. Would it be alright if I were to check in with you at some point in the future to see how you're doing?

IF YES: [Collect best contact information and thank for their time], continue to
Part E

IF NO: Thank you for speaking with me today. You are always welcome to reach out if you have any questions about anything we spoke about today, but we will not reach out in the future.

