STRIDE Intervention. The intervention content is included in Appendix 30.11. STRIDE is a brief, group-based, videoconference intervention with six weekly one-hour sessions and two follow-up 15-30-minute phone check-ins at month four and five. The STRIDE intervention incorporates aspects of *CBT for Adherence and Depression*,⁴¹ employing symptom management, cognitive restructuring, behavioral activation, and skills-based methods to address adherence and psychiatric symptoms. The first three sessions entail an assessment of patient, treatment, and healthcare system/provider barriers to adherence, followed by psychoeducation about breast cancer risk and benefits and risks of AET. We will employ specific interventions to target patient-identified barriers. For example, cognitive reframes will be applied to optimize accuracy related to recurrence risk perception and clinical necessity for therapy. Problem-solving will be implemented for management of financial distress (e.g., develop plan with social work and oncology team). To target healthcare system/provider barriers, the protocol will teach assertiveness skills for adopting an active role with clinicians and increasing self-efficacy. The last three tailored sessions will target treatment factors; patients will receive training in symptom management and coping strategies specific to the side effects or symptoms that they endorse. CBT is effective in helping patients manage cancer-related side effects such as pain, fatigue, and menopausal symptoms such as hot flashes. CBT strategies will address individual sources of distress, such as difficulty managing symptoms, or financial concerns around medication cost that are interfering with adherence and exacerbating distress. In extenuating circumstances, participants may be scheduled for individual sessions if we cannot schedule them for a group session within a reasonable amount of time.

Participants in the STRIDE intervention will continue to monitor medication-taking with the MEMS Caps throughout the 24-week study period. As part of the intervention, participants will practice relaxation training using study recordings through the study's website portal

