(stridestudy.mgh.harvard.edu). The structure of each website post can be viewed in Appendix 30.25. The website will move into production after IRB approval. This is a website created with the support of IT at MGH/HMS and is viewable to those with the link to the website URL. The website will contain no advertisements or other content. It will only contain the relaxation file, and the individual sessions from the work book that the intervention participants receive, so that they can also have an electronic version accessible for the future. Study staff will provide instructions for participants to access this website via email as part of the intervention session reminders (Appendix 30.14). In addition to the overall study PI, [name], trained clinical psychology practicum students, clinical psychology fellows, licensed psychologists or social workers on the study team at MGH will deliver the intervention, to ensure successful administration of the intervention. Interventionists will complete a post-intervention survey for each group intervention, which will document process variables such as session length, session interventionist, and session attendance. [name] has ample experience delivering this type of intervention and was a protocol therapist on several NIH-funded CBT-based studies. She will conduct weekly clinical supervision with trained interventionists. 80% of sessions will be audio-recorded and at least 10% randomly selected, stratified by interventionist, and reviewed with [name] for treatment fidelity. Content fidelity will be assessed by calculating the percentage of key intervention topics addressed out of total topics, with a goal of 90%.⁵¹ Feedback will be given to interventionists to enhance adherence to the protocol.

Finally, participants who identify as part of a racial/ethnic minority population will be offered the opportunity to participate in a qualitative exit interview to provide feedback on the STRIDE program.

Medication Monitoring Control. Participants in the comparison condition will not receive the STRIDE intervention; however, they will monitor medication-taking with MEMS Caps and undergo standard care with oncology follow-up.

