Hypothesis 1. We hypothesize that participation in the STRIDE intervention will be associated with an increase in adherence and satisfaction with AET and a decrease in symptom distress at 12-weeks compared to the medication monitoring control, and that these improvements will maintain at 24-week follow-up.

Data will be assessed for patterns of missingness⁷² and statistical assumptions. We will conduct mixed effects models with repeated measures data and relevant covariates such social support (MSPSS) and demographic and treatment-related factors (e.g., age, stage, time since AET initiation) as potential covariates. Longitudinal analyses will include all time points and a cross-sectional analysis for each time point. Given that this pilot is not powered to detect statistically significant group differences, we will examine mean differences and sample variability. Effect sizes (Cohen's d) will be calculated for changes in outcomes from baseline to four and eight months, as (Mean change score [intervention arm] – Mean change score [control arm])/SD pooled, where 0.3 indicates a small effect, 0.5 a medium effect, and 0.8 a large effect.⁷³ Effect sizes will be used in a power analysis to estimate the necessary sample size to conduct a full-scale efficacy trial with power >80%. We will also verify the needed sample size based on ability to detect a clinically meaningful difference and references to existing literature.⁷⁴

Exploratory Aim. To assess the effects of the STRIDE intervention on several psychosocial constructs, exploring potential mediator and moderators of the intervention.

Exploratory Hypothesis: We will explore whether participation in the STRIDE intervention is associated with an increase in QOL and medication-taking self-efficacy, and a decrease in distress (anxiety and depression at 12-weeks compared to the medication monitoring control, and whether these improvements are maintained at 24-week follow-up.

We will use the same procedure to assess changes in secondary outcomes in the intervention group. We will explore potential mediation of secondary and exploratory endpoints through changes in beliefs about adjuvant endocrine therapy (BMQ-AET) and/or perceived coping skills (MOCS), as well as self-efficacy for managing symptoms (Self-Efficacy For Symptoms).

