30.4 Study Telephone Recruitment Script

Hi, this is [Study Staff Name] calling from Massachusetts General Hospital. How are you today?

A1. Self-referral call-back: Thank you for reaching out to our study team regarding your interest in the STRIDE study. I would be happy to give you a brief overview of the study if you have a few minutes. Is now a good time?

IF YES: Continue to Section B.

IF NO: Is there a better time in the coming days I could give you a call back? [Continue to Section F.]

A2. Recruitment call: I am calling regarding a research study you might be eligible for and may have received a study flyer for while in-clinic last. Is now a good time that I could give you a brief overview of the study?

IF YES: Continue to Section B.

IF NO: Is there a better time in the coming days I could give you a call back? [Continue to Section F.]

B. Study Description

This study offers a program for women who are taking a hormonal therapy and consists of 6 weekly, small-group, virtual visits with a cancer center clinician to address any concerns or challenges you may be experiencing while taking this medication. Your oncologist said it would be alright if we speak with you about this study. These visits would take place over a secure videoconferencing software with a few other breast cancer survivors who are also taking hormonal therapy. Does this sound like something you might be interested in?

IF YES: Continue to Section C.

IF NO: Continue to Section F.

C. Eligibility Screening

Thank you for your interest; so, I have a few initial questions we like to ask to get a sense of if this study might be a good fit for you. All of these questions are optional and completely confidential.

Each question is scored on a scale of 0-10. The first question is, on a scale of 0 being not bothered at all to ten being extremely bothered, how bothered are you by side effects from your hormonal therapy?

My next question is, on a scale of 0 being not upset at all to ten being extremely upset, how upset are you by having to take hormonal therapy?

My last question is, on a scale of 0 being not difficult at all to 10 being extremely difficult, how difficult is it for you to take your hormonal therapy medication every day?

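### STRIDE is given in small groups by shared interventionists, but the secondary-outcome model names no group or interventionist term, so its standard errors may be modestly too small

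*Combined protocol and SAP*

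**What the plan says.** Section 9.2 describes the treatment: "STRIDE is a brief, group-based, videoconference intervention with six weekly one-hour sessions". The in-person screening script (Appendix 30.3) puts each woman in a session "with up to 2 other breast cancer survivors who are also taking hormonal therapy", that is, groups of at most three. The telephone script (Appendix 30.4) is looser: "with a few other breast cancer survivors who are also taking hormonal therapy". Section 9.2 also allows an exception, in that "participants may be scheduled for individual sessions if we cannot schedule them for a group session within a reasonable amount of time".

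Delivery is shared among several kinds of staff: "trained clinical psychology practicum students, clinical psychology fellows, licensed psychologists or social workers on the study team at MGH will deliver the intervention". Neither their number nor their caseload is given. A survey is completed for each group, "which will document process variables such as session length, session interventionist, and session attendance". Control participants use the electronic pill bottle and have standard oncology follow-up; they attend no sessions.

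For the secondary outcomes, Section 11.1 states: "We will conduct mixed effects models with repeated measures data and relevant covariates". The covariates it then lists (social support, age, stage, time since starting endocrine therapy) all belong to the individual woman. Sections 11.1 and 11.2 mention no therapy group, interventionist, ICC, design effect or robust standard error. Section 11.1 says the pilot is not powered for group differences. It will report mean differences, variability and Cohen's d, and will use the effect sizes to plan a full-scale trial with power above 80%.

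**The concern.** Women in the same STRIDE group share sessions, peers and a therapist for six weeks, while controls share none of these. The design is therefore partially nested: clustered in one arm and unclustered in the other. A model whose only correlation is between repeated measures on the same woman counts STRIDE women as more independent evidence than they are, and understates the variance of the STRIDE mean.

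The stake is the precision reported for the secondary and exploratory comparisons. That precision matters to the investigators, because Section 4.0 says accrual was raised from 75 to 100 to improve the ability to detect differences in secondary outcomes. The pilot is also meant to inform a larger trial of the same group-delivered treatment, and the sample size of that trial needs an allowance for clustering that the plan does not mention.

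**Working it through.** **The plan's own figures.** The only precision figures are the exact one-sided 95% lower limits for the feasibility rates in Section 11.1. For 64 of 80 (retention or attendance of 80%) the Clopper-Pearson limit is 71.2%, against 71% stated. For 80 of 134 (enrollment) it is 52.2%, against 53% stated, which is within one point. Neither involves the mixed model. No standard error or power is stated for the secondary comparison, so there is nothing there to reproduce.

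**Inputs.**
- Group size m: at most 3 (Appendix 30.3); m = 2 is taken as well, since groups need not be full.
- Women per arm: 100 randomised (Section 4.0). Equal allocation, 50 per arm, is assumed because no ratio is stated.
- ICC: not in the documents; 0.05, 0.10 and 0.20 are assumed.
- Interventionist clustering: not sized, because the number of interventionists and their caseload are not given.

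**Standard error of the arm difference.** The STRIDE-arm design effect is DE = 1 + (m − 1) × ICC, and the control arm has DE = 1. With equal arms, the ratio of correct to unclustered standard error is √((DE + 1)/2). Coverage of a nominal 95% interval is 2Φ(1.96/ratio) − 1.

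| m | ICC | DE | SE ratio | Coverage |
|---|---|---|---|---|
| 3 | 0.05 | 1.10 | 1.025 | 94.4% |
| 3 | 0.10 | 1.20 | 1.049 | 93.8% |
| 3 | 0.20 | 1.40 | 1.095 | 92.6% |
| 2 | 0.05 | 1.05 | 1.012 | 94.7% |
| 2 | 0.10 | 1.10 | 1.025 | 94.4% |
| 2 | 0.20 | 1.20 | 1.049 | 93.8% |

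For example, with m = 3 and ICC = 0.10: DE = 1 + 2 × 0.10 = 1.20, and √(2.20/2) = 1.049.

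**Effect on Cohen's d.** The plan divides the difference in mean change by the pooled SD, so no standard error enters. A simulation of 20,000 trials at each ICC, with 50 women per arm and 17 STRIDE groups (16 of three and one of two), gave a mean d of 0.50 to 0.51 for a true value of 0.50. The same runs gave SE ratios of 1.024, 1.050 and 1.096, which agree with the formula.

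**Next trial, if its calculation left clustering out.** Per-arm size at 80% power and two-sided 5% is (1.960 + 0.842)² × (1 + DE)/d². With DE = 1 this gives 175 at d = 0.3 and 63 at d = 0.5. For groups of three at ICC 0.05, 0.10 and 0.20 it gives 184, 192 and 210 at d = 0.3, and 66, 70 and 76 at d = 0.5. A trial run at the unclustered size would have 78.2%, 76.3% and 72.6% power.

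**Can the pilot supply the ICC?** Take 17 groups of three. At a true ICC of 0.05 the expected variance ratio is F = 1 + 3 × 0.05/0.95 = 1.158, on 16 and 34 degrees of freedom. Dividing by the F quantiles 2.220 and 0.394 and converting by (F − 1)/(F + 2) gives a 95% interval of about −0.19 to 0.39. The estimate is zero or below with probability about 39%, or about 27% at a true ICC of 0.10.

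**The case against.** Four points can fairly be made for the plan.

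- A reader might infer that the plan declares STRIDE women independent. It does not. The random effects are unspecified, and a statistician could add a group term without contradicting the text. This stands as a limit on wording: the supportable statement is that no clustering term is named. It does not remove the point, because nothing in the plan would prompt anyone to add one.
- A reader might infer that the full trial will be under-sized. The documents do not support that. The quantity carried forward is Cohen's d, which clustering barely affects; the later calculation is not in these documents; and Section 11.1 adds a check against a clinically meaningful difference and the literature. The power figures above describe an omission that might be made, not one that has been made. The check does not itself supply a design effect, however.
- The effect is small and rests on assumed inputs. Three is the maximum group size and some women may be seen individually. With 50 per arm, the sampling standard error of d is already about √(2/50) = 0.20, which dwarfs an inflation of a few per cent. This stands, and it sets the weight of the point.
- The pilot is openly unpowered for these comparisons, and its primary endpoint is feasibility and acceptability. This also stands, though the reason given for raising accrual to 100 shows that secondary precision is not irrelevant.

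**Conclusion.** The point holds in a limited form. STRIDE is clustered by group and interventionist in one arm only, and the named model makes no provision for it. If it is fitted as described and the ICC is above zero, standard errors for the secondary and exploratory arm differences are modestly too small, by the amounts in the table: about 1% to 5% at ICC 0.05 to 0.10, and up to 9.5% at ICC 0.20 in full groups of three. These figures rest on an assumed ICC, equal allocation and equal group sizes; individual delivery would reduce them. Any additional interventionist effect cannot be sized from the documents.

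Cohen's d and the primary feasibility endpoint are not affected through this model. Under-sizing of the next trial is a risk only if its calculation omits a design effect. This is a change the plan should make, not a flaw that undermines the pilot.

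**What to change.** In Section 11.1, specify a partially nested mixed model for the secondary and exploratory outcomes: the repeated-measures structure already planned, plus a random effect for therapy group in the STRIDE arm only, with controls and individually treated women as clusters of one. Report the group ICC with its interval, and say in advance that it will be too imprecise to use alone. Summarise outcomes by interventionist descriptively.

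For the full trial, state that the STRIDE-arm sample size will be multiplied by 1 + (m − 1) × ICC over a range of assumed ICCs. With n controls and DE × n STRIDE women, the variance is DE × σ²/(DE × n) + σ²/n = 2σ²/n, which restores the planned precision. At d = 0.5, m = 3 and ICC 0.05, that is 63 × 1.10 = 69.3, so 70 STRIDE women against 63 controls.

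The cost is one extra variance term, which will often be estimated at zero, and slightly wider intervals. No new data collection should be needed, since a survey recording interventionist and attendance is already completed for each group.
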